8.1.1. Disease Assessment - Response Criteria in AML

The response criteria in AML (Döhner et al, 2017) are as follows in Table 6Relapse includes either hematologic and/or molecular relapse as defined in Table 6 at any disease assessment.

Confidential Page 43 of 74

Table 6. Response Criteria in AML

Category	Definition
CR without minimal residual disease $(CR_{MRD}$ -)	If studied pretreatment, CR with negativity for a genetic marker by quantitative reverse transcription polymerase chain reaction (RT-qPCR), or CR with negativity by multiparameter flow cytometry (MFC) and/or molecular testing
Complete remission (CR)	Bone marrow blasts <5%; a bsence of circulating blasts and blasts with Auer rods; a bsence of extramedullary disease; a bsolute neutrophil count \geq 1.0 x 10 $^9/L$ (1000/µL); platelet count \geq 100 x 10 $^9/L$ (100,000/µL) Note: MRD $^+$ or unknown
CR with incomplete recovery (CR _i)	All CR criteria except for residual neutropenia ($<1.0 \times 10^9/L [1000/\mu L]$) or thrombocytopenia ($<100 \times 10^9/L [100,000/\mu L]$)
Morphologic leukemia-free state (MLFS)	Bone marrow blasts <5%; absence of blasts with Auer rods; absence of extramedullary disease; no hematologic recovery required
Partial remission (PR)	All hematologic criteria of CR; decrease of bone marrow blast percentage to 5 to 25 percent; and decrease of pretreatment bone marrow blast percentage by at least 50 percent
Treatment failure	
Primary refractory disease	No CR or CR _i a fter 2 courses of intensive induction treatment; excluding patients with death in a plasia or death due to indeterminate cause
Death in a plasia	Deaths occurring ≥7 days following completion of initial treatment while cytopenic; with an aplastic or hypoplastic bone marrow obtained within 7 days of death, without evidence of persistent leukemia
Death from indeterminate cause	Deaths occurring before completion of therapy, or <7 days following its completion; or deaths occurring ≥7 days following completion of initial therapy with no blasts in the blood, but no bone marrow examination available
Response criteria fo	
Stable disease ^a	Absence of CR _{MRD} -, CR, CR _i , PR, MLFS; and criteria for PD not met
Progressive disease (PD)	Evidence for a n increase in bone marrow blast percentage and/or increase of a bsolute blast counts in the blood: >50% increase in marrow blasts over baseline (a minimum 15% point increase is required in cases with <30% blasts at baseline; or persistent marrow blast percentage of >70% over at least 3 months; without at least a 100% improvement in ANC to an a bsolute level (>0.5 x 10^9 /L [500/µL], and/or platelet count to >50 x 10^9 /L [50,000/µL] nontransfused); or >50% increase in peripheral blasts (WBC X% blasts) to >25 X 10^9 /L (>25,000/µL) (in the absence of differentiation syndrome); or New extramedullary disease
Relapse	
Hematologic relapse (a fter CR _{MRD} -, Cr, CR _i)	Bone marrow blasts ≥5%; or reappearance of blasts in the blood; or development of extra medullary disease
Molecular relapse (after CR _{MRD} -)	If studied pretreatment, reoccurrence of MRD as a ssessed by RT-qPCR or by MFC

^a The period of stable disease should be at least 3 months to be considered SD.

Confidential Page 44 of 74

8.2. Safety Assessments

Planned time points for all safety assessments are provided in the SoA (Table 1).

8.2.1. GVHD Assessments

A potential toxicity for patients receiving allogeneic T cells is GVHD. The risk that adoptively transferred leukemia-targeted T cells will cause GVHD is very low. GVHD will be assessed as per SoA (Table 1) and as per acute and chronic GVHD guidelines (Harris et al 2016; Jagasia et al, 2015).

8.2.2. Vital Signs

Vital signs will be evaluated at specified time points as indicated in SoA (Table 1).

Temperature, pulse rate, and blood pressure will be assessed, and if clinically indicated, respiratory rate will also be assessed.

8.2.3. Clinical Laboratory Assessments

See the SoA (Table 1) for the timing and frequency of clinical laboratory tests to be performed. Laboratory tests to be collected (on days of MT-401 administration, labs should be performed prior to MT-401 administration): complete blood count and differential, glucose, calcium, magnesium, phosphorus, blood urea nitrogen, creatinine, bilirubin (total and direct), alanine aminotransferase, aspartate aminotransferase, alkaline phosphatase, sodium, potassium, chloride, carbon dioxide, albumin, and total protein. The baseline laboratory test results for clinical assessment for a particular test will be defined as the last measurement prior to the initial dose of MT-401. Additional tests may be performed at any time during the study as determined necessary by the investigator or required by local regulations.

- The investigator must review the laboratory report, document this review, and record any clinically relevant changes occurring during the study in the AE section of the eCRF with assistance of site personnel. The laboratory reports must be filed with the source documents. Clinically significant abnormal laboratory findings are those that are not associated with the underlying disease, unless judged by the investigator to be more severe than expected for the patient's condition.
- All laboratory tests with values considered clinically significantly abnormal during participation in
 the study or within 30 days after the last dose of MT-401 should be repeated until the values return to
 normal or baseline or are no longer considered clinically significant by the investigator or medical
 monitor.
- If such values do not return to normal/baseline within a period of time judged reasonable by the investigator, the etiology should be identified and the Sponsor notified.
- If laboratory values from non-protocol specified laboratory assessments performed at the institution's local laboratory require a change in patient management or are considered clinically significant by the investigator (e.g., SAE or AE or dose modification), then the results must be recorded in the eCRF.

Confidential Page 45 of 74

8.2.4. History and Physical Examinations

History and physical examinations will be performed at specified time points as indicated in the SoA (Table 1). A complete physical examination will be performed as per institutional guidelines but at baseline will include, at a minimum, assessments of the Cardiovascular, Respiratory, Gastrointestinal and Neurological systems, and height (at Screening) and weight will also be measured and recorded.

- A brief physical examination will include, at a minimum, assessments of the Cardiovascular, Respiratory, and Gastrointestinal systems (height and weight will be needed at screening at minimum and any changes recorded if >10%).
- Investigators should pay special attention to clinical signs related to previous serious illnesses.

8.3. Adverse Events and Serious Adverse Events

An AE is any untoward medical occurrence in a patient or clinical study patient, temporally associated with the use of MT-401, whether or not considered related to MT-401. An AE can therefore be any unfavorable and unintended sign (including an abnormal laboratory finding), symptom, or disease (new or exacerbated) temporally associated with the use of MT-401. The NCI CTCAE (Version 5.0) for Adverse Events will be utilized for AE reporting. The criteria listed in the Cancer Therapy Evaluation Program (CTEP) NCI Common Toxicity Criteria Scale will be used in grading toxicity, with the exception of CRS toxicity and neurotoxicity that are related to T-cell infusions. CRS toxicity will be graded according to Table 13 (as per Lee et al, 2019 which also contains assessment of neurotoxicity). The CTEP CTCAE is identified and located on the CTEP website at:

http://ctep.cancer.gov/protocolDevelopment/electronic applications/ctc.htm.

AEs will be reported by the patient (or, when appropriate, by a caregiver, surrogate, or the patient's legally authorized representative). In addition, the investigator (or designee) is responsible for detecting, documenting, and recording events that meet the definition of an AE or SAE and remain responsible for following up AEs that are serious, considered related to MT-401 or study procedures, or that caused the patient to discontinue treatment or the study (see Section 7).

If an event is not an AE, then it cannot be an SAE even if serious conditions are met (e.g., hospitalization for signs/symptoms of the disease under study, death due to progression of disease or planned procedures/surgeries).

An SAE is defined as any untoward medical occurrence that, at any dose:

- Results in death
- Is life-threatening (that is, immediate risk of dying)
- Requires inpatient hospitalization or prolongation of existing hospitalization
- Results in persistent or significant disability/incapacity
- Is a congenital anomaly/birth defect
- Is considered significant by the investigator based on appropriate medical judgement

Confidential Page 46 of 74

8.3.1. Period and Frequency for Collecting AE and SAE Information

All AEs will be collected from Day 0 until the Week 12 Visit at the time points specified in the SoA (Table 1), after which only treatment-related AEs and SAEs will be noted.

All SAEs from Baseline Visit to Week 12 Visit will be recorded and reported to the Sponsor or designee immediately and under no circumstance should this exceed 24 hours of learning of the event, as indicated in Appendix 1, Section 11.1. The investigator will submit any updated SAE data to the Sponsor within 24 hours of it being available. Additionally, any patient with any grade CRS or neurotoxicity will be reported in an expedited fashion within 24 hours of learning of event.

Investigators are not obligated to actively seek AEs or SAEs after conclusion of the study participation. However, if the investigator learns of any SAE, including a death, at any time after a patient has been discharged from the study, and he/she considers the event to be at least possibly related to the study intervention or study participation, the investigator must promptly notify the Sponsor.

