c Intervention Period includes study treatment and Active Follow-up and Survival Follow-up as defined in Section 4.4 (including for Safety Lead-in portion of the study). Day 0/Week 0 is considered the day of the first infusion of MT-401 (which differs from the Day 1 used for allogeneic HSCT). Each infusion and visit must be at least 2 weeks apart. Active Follow-up Period as defined in Section 4.4: occurs after the last dose of MT-401 has been administered until patient relapses/progresses or declines additional study visits. Timing of Follow-up Visits are in relation to the timing of the Day 0 visit. Sponsor will schedule Day 0 timing for all patients in all groups, including Group 1 SoC arm.

d SoC patients do not need to perform visit Weeks 2 or 4, unless clinically indicated. Week 0 visit for SoC patients may occur between days 85-130 post-HSCT, as instructed by Sponsor.

^e Survival follow-up begins after relapse/progression or active follow-up is completed and occurs every 3 months for 3 years, every 6 months for the remainder of the study (which can be phone contact to collect patient survival status [if alive, last date known alive, and if dead, date of death], and collect any additional anticancer therapy post-MT-401 or SoC received during study.

Confidential Page 19 of 74

f Brief physical exam, to include at a minimum, assessments of the Cardiovascular, Respiratory, and Gastrointestinal systems (height and weight will be needed at screening at minimum and any changes recorded if >10%).

g Pregnancy testing is required unless a patient has no possibility of being pregnant (for example post-hysterectomy). Perform as clinically indicated during intervention period for WOCBP. See Section 8.3.5 for details.

^h On day of MT-401 administration, laboratory assessments and/or disease assessments are completed prior to infusion (see Section 8.2.3 for additional details of laboratory assessments to be performed).

¹ Vital signs obtained within 1 hour pre- and post-infusion (window ± 15 min).

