Study treatment is administered for all patients (except SoC - Group 1- Arm B) on Day 0 and every 2 weeks for a planned maximum of 3 doses. Patients randomized to SoC (Group 1B) at 80 days post-transplant may crossover to the relapse group (Group 2) if the patient is found to have relapse of disease (MRD* or frank relapse) and the subgroup is open and/or Sponsor agreement. After relapse and prior to bridging chemotherapy, the patient should perform assessments associated with the Screening visit if not already completed. The patient should perform the assessments associated with Baseline following bridging chemotherapy and prior to MT-401 administration. The patient will have their visits reset and have their MT-401 administered on Day 0 and follow the schedule of events from that point forward. Group 1- Arm B (SoC) patients will continue to follow the SoA minus administration of MT-401. Refer to Section 6 for additional dosing details. Administration of MT-401 can be delayed due to management of AEs or other toxicities, but patients should resume T cell infusions within 2 weeks of their scheduled dose. If greater than 2 weeks is needed, Sponsor will determine if patient can resume T cells infusions.

m All AEs and SAEs, from Day 0 and Baseline, respectively, to the Week 12 Visit will be collected; after Week 12, only treatment-related AEs and SAEs will be collected.

ⁿ Detailed studies outlined in Section 8.8.

o Additional details regarding the PRO questionnaire and associated instructions will be provided in a separate document.

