6.6. Dose Modification

No dose modifications will be allowed except in rare instances of manufacturing constraints, and any other issues specifically discussed with the Sponsor. As a result, patients may receive either lower or higher than the intended doses; these patients will complete the study but will be evaluable in a separate sub-group.

Timing of MT-401 administration (at least 2 weeks apart) may be modified for 1 week due to inclement weather, vacation, etc., but any longer durations need to be discussed with the Sponsor. Administration of MT-401 can also be delayed due to management of AEs or other toxicities, but patients should resume T cell infusions within 2 weeks of their scheduled dose. If greater than 2 weeks is needed, Sponsor will determine if patient can resume T cells infusions. All dose modifications should be documented, including the approach taken and a clear rationale for the need for modification. Additionally, the investigator must assess if a toxicity is considered attributable to T cells. If MT-401 is available for a patient, a patient may be re-dosed if requested by the investigator and approved by the Sponsor on a case-by-case basis.

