9.3.5. Safety Analyses

Safety and toxicity outcomes including treatment-emergent AEs, CRS, GVHD, neurological findings, and laboratory evaluations will be summarized using descriptive statistics for all patients in the All treated population by group. Safety evaluations will be based on the incidence, intensity, and type of AEs or SAEs, as well as changes in the patient's physical examination findings, vital signs, and clinical laboratory results.

AEs will be assessed for severity according to the U.S. NCI CTCAE, Version 5.0, and the verbatim AE terms will be coded using the Medical Dictionary for Regulatory Activities (MedDRA Version 25 or higher) for purposes of summarization.

The safety analysis will be performed in all treated patients. Descriptive statistics of safety will be presented by dose cohort or by treatment arm. All on-treatment AEs, drug-related AEs, late-emergent drug-related AEs, SAEs and drug-related SAEs will be tabulated using worst grade per NCI CTCAE Version 5.0 criteria by system organ class and preferred term. On-study laboratory parameters including hematology, chemistry, liver function and renal function will be summarized using worst grade per NCI CTCAE Version 5.0 criteria.

All deaths within 30 and 60 days of the last dose of MT-401 will be summarized. For Group 1 SoC arm, deaths within 30 days and 60 days of randomization date plus average time from randomization to last dose in the MT-401 arm will also be summarized as reference.

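### Full AE collection ends at a Week 12 Visit counted from the first infusion, not the last, and the open-ended SAP TEAE tables then add attributed events that only the MT-401 arm can have

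*Protocol*

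**What the plan says.** **Collection window.** Protocol 8.3.1: "All AEs will be collected from Day 0 until the Week 12 Visit at the time points specified in the SoA". SAEs start earlier, at Baseline, and 8.3.1 again names the Week 12 Visit as the end point for recording all of them. The Schedule of Activities (Protocol 1.3, footnote m) adds: "after Week 12, only treatment-related AEs and SAEs will be collected".

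**Clock.** Footnote c of the same table: "Day 0/Week 0 is considered the day of the first infusion of MT-401", and "Timing of Follow-up Visits are in relation to the timing of the Day 0 visit". The Week 12 Visit has a window of ±1 week. A reset of the visit schedule is described only for Arm B patients who cross over to Group 2.

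**Dosing.** MT-401 is given "on Day 0 and every 2 weeks for a planned maximum of 3 doses", with infusions at least 2 weeks apart. After a delay for toxicity, Protocol 6.6 says "patients should resume T cell infusions within 2 weeks of their scheduled dose". Longer delays are left to the Sponsor, with no upper limit given. Section 6.6 also says "a patient may be re-dosed if requested by the investigator and approved by the Sponsor on a case-by-case basis". No AE window is given for re-dosing.

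**Analysis.** SAP 7.1.5 defines TEAEs by onset or worsening after the first dose (MT-401) or after randomization (Group 1 SOC). It sets no end date for either. SAP 7.5.2 summarises them by treatment group. Protocol 9.3.5 names on-treatment AEs and late-emergent drug-related AEs as separate tabulations. Neither document defines the second category, and the SAP does not carry it over.

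**The concern.** Two separate problems follow from these rules.

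First, the stretch of full AE collection after the last exposure is whatever remains of a fixed 12 weeks, so it shrinks with every week the last infusion slips. Protocol 11.1.2 expects that immune-related events may appear as late as several months after the last dose. Once Week 12 has passed, an event enters the database only if an open-label investigator attributes it to treatment. The plan has rules for re-treatment in the efficacy analyses (Protocol 9.3; SAP 7.1) but no matching rule for safety.

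Second, Group 1 is a randomized comparison with an observation arm. Up to Week 12 both arms report all AEs. Afterwards the criterion is relatedness to a product that Arm B does not receive. A TEAE table with no end date pools the two periods. A reader comparing the columns would see a difference produced partly by the collection rule.

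**Working it through.** The documents state no length of AE follow-up after the last dose, so there is no planned figure to reproduce. The check on the window is calendar arithmetic.

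**Inputs.** Week 12 Visit at V = 11, 12 or 13 (Protocol 1.3). Planned doses at Weeks 0, 2 and 4. Toxicity delay of up to 2 weeks per dose (Protocol 6.6). Minimum spacing of 2 weeks (Protocol 1.3, footnote c).

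**Formula.** Weeks of full collection after dose 3 = V − D3, where D3 is the week of dose 3.

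- If the 2-week limit runs from the Schedule of Activities week, D3 = 4 + b, with b the lateness of dose 3 and b ≤ 2. Dose 2 at Week 4 and dose 3 at Week 6 still respects the spacing, so D3 is at most 6.
- If dose 3 is re-based on the actual date of dose 2, D3 = 4 + a + b, with a and b the delays of doses 2 and 3. Each is at most 2, so D3 is at most 8.

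| Case | D3 | Weeks left, V = 11 / 12 / 13 | Days left |
|---|---|---|---|
| On schedule | 4 | 7 / 8 / 9 | 49 / 56 / 63 |
| Limit from the scheduled week, used in full | 6 | 5 / 6 / 7 | 35 / 42 / 49 |
| Re-based, both delays used in full | 8 | 3 / 4 / 5 | 21 / 28 / 35 |
| Illustration: Sponsor agrees to 3 weeks each, re-based | 10 | 1 / 2 / 3 | 7 / 14 / 21 |

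The last row is an assumption, because the documents give no figure for longer delays. Re-dosing after the Week 12 Visit leaves 0 weeks of full collection. Re-dosing before it keeps whatever days remain.

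**Effect of a 30-day floor.** Extra days = max(0, 30 − days left). This gives 0 in the first two rows, 9 / 2 / 0 in the third (30 − 21, 30 − 28, none) and 23 / 16 / 9 in the fourth (30 − 7, 30 − 14, 30 − 21).

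**The between-arm tables.** No arithmetic applies, so the rules are set side by side:

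| | Arm A (MT-401) | Arm B (observation) |
|---|---|---|
| AEs collected to Week 12 | all | all |
| AEs collected after Week 12 | treatment-related | none can be MT-401-related |
| SAP TEAE end date | none | none |
| Tabulated together | yes, by treatment group | yes |

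The optional Group 1 sensitivity summary in SAP 7.5.2 starts the count at randomization. It changes the start of the period and leaves its end open, so it does not remove the difference.

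**The case against.** The strongest reply is that the window was set deliberately and works for nearly everyone. Amendment 5 wrote it in. Every treated patient has the same Day 0 to Week 12 window, events during a toxicity delay are fully captured, and Protocol 7.1 bars a patient with a DLT from further treatment. On the more literal reading of the delay rule, at least 35 days of full collection remain after dose 3. For Group 1, SoC safety data are shown only for reference (Protocol 9.2), no between-arm safety test is planned, related events already have their own SAP tables, and Protocol 9.3.5 already separates late-emergent drug-related AEs.

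Much of this stands, and it rules out several stronger readings that a reader might infer:

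- *Three weeks is what delayed patients get.* It needs two full delays, re-basing of dose 3 and a Week 12 Visit one week early. It is not an absolute minimum either, since the Sponsor may allow longer delays.
- *Patients delayed for toxicity are followed for less time.* Their total window is unchanged. Only the part after the last infusion shortens.
- *Re-dosed patients have no safety follow-up.* After Week 12, related events, expedited CRS and neurotoxicity reports, GVHD assessments, laboratory tests and deaths are still collected. The documents are silent on full AE collection after re-dosing rather than excluding it.
- *The plan breaks its own 30- and 60-day windows.* Those serve other purposes: "All deaths within 30 and 60 days of the last dose of MT-401 will be summarized", and in Protocol 8.2.3 the repeating of abnormal laboratory tests for 30 days. Even the on-schedule case (49-63 days) can fall short of 60.
- *Arm B contributes nothing after Week 12.* The phrase in footnote m could be read as keeping all SAEs. The SAE sentence in 8.3.1, which ends at Week 12, makes the narrower reading more likely but does not settle it. Crossover patients also start a new window.

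Two gaps survive. Nothing links collection to the last infusion when delays are long or a patient is re-dosed. The late-emergent category is named without a definition and is missing from the SAP, so as written the tables still pool the two periods.

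**Conclusion.** The point holds in a limited form. Full AE collection after dose 3 is 7-9 weeks on schedule. With delays inside the 2-week limit it is 5-7 or 3-5 weeks, depending on how the scheduled dose is read. It is shorter after longer Sponsor-agreed delays, and zero after re-dosing that follows Week 12. The practical shortfall is therefore confined to long or stacked delays and to re-dosing. Most patients are unaffected.

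The Group 1 table problem does not depend on any delay. It follows from the collection rule and the TEAE definition as written, and treatment-attributed events after Week 12 can add only to the MT-401 column. Its size cannot be given, because the documents contain no late-event rates. For SAEs it rests on the narrower reading of the collection phrase.

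This should be corrected before the tables are programmed. It does not threaten the efficacy analyses.

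**What to change.** 1. **SAP 7.1.5 and 7.5.2.** End the Group 1 between-arm TEAE tables at the Week 12 Visit in both arms. The Sponsor schedules Day 0 for the SoC arm too (Protocol 1.3, footnote c), so the same cut can be applied there. Present later related events for MT-401 separately as the late-emergent drug-related category of Protocol 9.3.5, and define that category.
2. **Protocol 8.3.1 and footnote m.** Collect all AEs and SAEs until the later of the Week 12 Visit and 30 days after the last MT-401 infusion, including any re-dosing. State whether unrelated SAEs are collected after Week 12.

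Both changes concern data collection and tabulation only, not dosing or clinical management. The cost is a short amendment, a few more weeks of AE entry for patients with long delays or re-dosing, and one date cut in the tables. Patients dosed on schedule are not affected by the 30-day floor.
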